## PROTOCOL SYNOPSIS

Name of Sponsor/Company:
Insys Development Company, Inc.
Name of Investigational Product:
Cannabidiol Oral Solution
Name of Active Ingredient:
Cannabidiol
Title of Study:
A Multicenter, Open-label, Flexible Dose Study to Assess the Long-Term Safety of Pharmaceutical Grade Synthetic Cannabidiol Oral Solution in Pediatric Patients with Treatment-Resistant Childhood Absence Seizures
Study center(s): Prospectively 8 sites will screen patients for enrollment
Phase of development: Phase 2 Long-Term Safety
Objective:
The objective of this study is to assess the long-term safety and tolerability of Cannabidiol Oral Solution (CBD) in pediatric patients with treatment-resistant Childhood Absence Seizures.
Methodology:
This is a multicenter, open-label, flexible dose study designed to assess long-term safety and tolerability of CBD in doses ranging from 20 mg/kg/day to 40 mg/kg/day in patients with treatment-resistant childhood absence seizures. Patients must have completed INS011-17-103 to be eligible.
The Investigator will ensure that the patients legal representative [parent(s)/caregiver(s)] will receive a copy of the informed consent form for review and provide full informed consent prior to study participation. Patients may enroll in the Long-Term Safety study (INS011-17-113) after completing INS011-17-103 Visit 6 (End of Study) to avoid interruption of the investigational product. Patients will have up to 2 weeks to enroll in INS011-17-113. The first visit (Visit 1) for INS011-17-113 will be after the completion of Visit 6 of INS011-17-103.
Patients will continue to receive CBD treatment for approximately 48 weeks. Patients will remain on their previously assigned dose from Study INS011-17-103 or may be titrated up to a higher dose level if the Data Monitoring Committee (DMC) has approved the higher dose level in INS011-17-103. If any participant does not enroll within the 2 week window, that patient will not be eligible to enroll into the study.
The study will consist of a Safety Period (48±2 weeks), Taper Period (10±3 days), and a Follow-up Period (30±5 days). Treatment visits will be scheduled monthly for the first

3 months and then quarterly over the remaining 9 months. All patients will complete a Visit 7 (End of Study) or Early Withdrawal Visit regardless of when they stop treatment/complete the study. A Follow-Up telephone call (Visit 9) will occur 30 days after the end of either the End of Study (Visit 7) or Early Withdrawal.

In this study, all patients will be dosed as follows:

- Once the informed consent for INS011-17-113 is provided within the required time frame, initially the patient will receive the same dose as was administered during INS011-17-103. If tolerability issues occurred during INS011-17-103, the dose can be decreased if the dose was greater than 20 mg/kg/day. If the patient received 20 mg/kg/day and the physician wants to decrease the dose, the patient should be discontinued.
- Physicians will not increase a patient's assigned dose until the Data Monitoring Committee has deemed that the higher dose is safe in INS011-17-103. Doses of CBD may be adjusted at the investigator's discretion up to a maximum of 40 mg/kg/day.
- Treatment with established antiepileptic drugs (AEDs) and therapeutic treatments (e.g., vagus nerve stimulation [VNS]) may be initiated/continued/adjusted and changes will be permitted as necessary based on safety concerns or changes in seizure control. Any changes must be documented in the eCRF.

Patients will be dosed approximately every 12 hours with food to help ensure consistent plasma levels are achieved. Patients will be dosed for 48 weeks during which the investigator will assess safety and tolerability.

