### **3.4. Dose Adjustment Criteria**

Doses of CBD may be adjusted at the investigator's discretion up to a maximum of 40 mg/kg/day only if the Data Monitoring Committee has approved the higher dose level in INS011-17-103. Doses greater than 40 mg/kg/day are not allowed. All dose changes must be clearly documented in the eCRF.

Antiepileptic drugs (AEDs) or therapies (e.g., VNS and ketogenic diet) may be initiated, discontinued or dose adjusted as needed. Any changes must be documented in the eCRF.

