## 4. TREATMENTS

### 4.1. Treatments Administered

Patients or parent/caregiver will be reminded how to measure, take their dose, and record their dose in the dosing diary when the IP is dispensed for the first time.

Total daily doses ranging from 20 mg/kg/day to 40 mg/kg/day will be administered with food, within 30 minutes after a meal, in two equivalent daily doses approximately every 12 hours.

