#### 6.1.8.2. Classification of Adverse Events

Adverse events are to be recorded on the AE page of the patient's case report form (CRF). Severity will be graded according to the following definitions:

- **Mild:** The patient experiences awareness of symptoms but these are easily tolerated or managed without specific treatment.
- **Moderate:** The patient experiences discomfort enough to cause interference with usual activity, and/or the condition requires specific treatment.
- **Severe:** The patient is incapacitated with inability to work or do usual activity, and/or the event requires significant treatment measures.

Action taken will be categorized as none, study drug discontinued, dose modified, required concomitant medication, required procedure, or other.

Event outcome at resolution or time of last follow-up will recorded as event resolved, resolved with sequelae, ongoing, or death.

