#### 8.4.1. Study Patients and Demographics

##### 8.4.1.1. Disposition and Withdrawals

The numbers of patients entering, completing, and withdrawing, along with reasons for withdrawal, will be tabulated overall and by modal dose group. For each patient, the modal dose is the dose with the longest exposure during the study.

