##### **8.4.3.1. Adverse Events**

The Medical Dictionary for Regulatory Activities (MedDRA, version 20.0 or higher) will be used to classify all AEs. Adverse event summaries will include only TEAEs, which will be summarized for each modal dose group. For each patient, the modal dose is the dose with the longest exposure during the study.

The number and percentage of patients with AEs will be displayed for each treatment group by system organ class and preferred term. Summaries of AEs by severity and relationship to the IP will also be provided. Serious AEs (SAEs) and AEs resulting in discontinuation will be summarized separately in a similar manner. Patient listings of AEs and SAEs will be produced.

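### Withdrawals and AEs leading to discontinuation are tabulated by modal dose, but step-down is open only above 20 mg/kg/day, so the lowest dose can look least tolerable; no table of dose reductions is planned.

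*Combined protocol and SAP*

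**What the plan says.** **Dosing.** The synopsis (Methodology) and Section 3.1 deal with patients who had tolerability problems in INS011-17-103: "the dose can be decreased if the dose was greater than 20 mg/kg/day". The next sentence covers the lowest dose: "If the patient received 20 mg/kg/day and the physician wants to decrease the dose, the patient should be discontinued". For the study itself, Section 4.1 sets the range ("Total daily doses ranging from 20 mg/kg/day to 40 mg/kg/day will be administered with food") and Section 3.4 leaves changes to the investigator ("Doses of CBD may be adjusted at the investigator's discretion up to a maximum of 40 mg/kg/day"), with all dose changes recorded in the eCRF.

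**Analysis.** Section 8.4.1.1 tabulates patients entering, completing and withdrawing; these counts, "along with reasons for withdrawal, will be tabulated overall and by modal dose group". It defines the grouping: "For each patient, the modal dose is the dose with the longest exposure during the study". Section 8.4.3.1 builds the TEAE tables on the same modal dose groups and adds "Serious AEs (SAEs) and AEs resulting in discontinuation will be summarized separately in a similar manner".

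**Collection.** Section 6.1.8.2 records what was done about each AE: "Action taken will be categorized as none, study drug discontinued, dose modified", followed by further categories. No part of Section 8 summarizes dose reductions, or AEs that led to them, by any definition of dose.

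**The concern.** A patient who cannot tolerate 30 or 40 mg/kg/day has a way to stay in the study on less drug. A patient who cannot tolerate 20 does not, if the 20 to 40 range is kept. Equal intolerance thus becomes a discontinuation at the lowest dose and, some of the time, a dose change at the higher ones. The planned by-dose tables count only discontinuations.

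Tolerability is half of the single study objective (Section 2). Section 1.3 already describes the earlier extension study by the share of subjects tolerating 40 mg/kg/day, and reports several AEs that rose with dose in the preceding PK study. A reader will naturally look at the withdrawal table for a dose gradient. The table can flatten that gradient or turn it round, and nothing beside it shows the reductions that explain why.

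**Working it through.** The plan gives no power, error rate or expected intolerance rate, so there is no planned figure to reproduce. The sample size is a roll-over cap of 30 (Section 8.2).

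**Inputs from the documents:** step-down possible above 20 mg/kg/day and not at 20; range 20 to 40; dose levels 20, 30 and 40; 48 weeks of treatment; grouping by dose of longest exposure.

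**Assumptions not in the documents:**
- 10 patients start on each dose.
- q is the chance of intolerance on the starting dose over 48 weeks, with onset uniform in time.
- s is the chance that an intolerant patient above 20 steps down by 10 mg/kg/day; otherwise the patient withdraws. At 20 the patient withdraws.
- r is the chance of intolerance again after each step-down, with onset uniform over the remaining time; r = 0.1 to 0.3.

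**Step 1, by starting dose.** The share of intolerant patients who finally withdraw is:
- from 20: 1
- from 30: f = (1 − s) + s·r
- from 40: g = (1 − s) + s·r·f

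With q = 20%:
- s = 0.5: f = 0.55 to 0.65, so 30 mg/kg/day shows 11 to 13%. g = 0.5275 to 0.5975, so 40 shows 10.6 to 12.0%.
- s = 0.8: f = 0.28 to 0.44, so 30 shows 5.6 to 8.8%. g = 0.2224 to 0.3056, so 40 shows 4.4 to 6.1%.

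The 20 mg/kg/day group shows 20% throughout.

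**Step 2, by modal dose as planned.** Regrouping moves some patients: those who step down early count at the lower dose, those who step down late stay at the higher one. Simulation (3,000 trials per scenario), withdrawals in %:

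| True intolerance 20/30/40 | s | 20 | 30 | 40 | 20 strictly highest |
|---|---|---|---|---|---|
| 20/20/20 | 0 | 20 | 20 | 20 | 24-25% of trials |
| 20/20/20 | 0.5 | 20 | 11-13 | 11-12 | 47-52% |
| 20/20/20 | 0.8 | 19-20 | 5.5-8 | 5-6 | 66-70% |
| 20/20/20 | 1.0 | 19-20 | 1.5-5 | 0.1-1 | 81-87% |
| 15/20/30 | 0.5 | 15 | 11-12.5 | 17-18 | 26-29% |
| 15/20/30 | 0.8 | 15 | 5-8 | 7.5-9 | 49-54% |

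**Step 3, when the order reverses.** By starting dose and for a single step, 20 shows more withdrawals than a higher dose unless q_high/q_20 exceeds 1/f. That break-even ratio is 1.5 to 1.8 at s = 0.5, 2.3 to 3.6 at s = 0.8 and 3.3 to 10 at s = 1.0. With rates of 15/20/30% and s = 0.5, the 40 mg/kg/day group still looks worst; with s = 0.8 the 20 group does.

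**Step 4, counting reductions too.** If the event is the first dose reduction or withdrawal for intolerance, assigned to starting dose, each group returns its own q by construction: 20/20/20% or 15/20/30%.

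**The case against.** The strongest points on the other side are these.

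- *The explicit rule is an entry rule.* The step-down sentence concerns tolerability in INS011-17-103. A patient discontinued before any dose in this study has no modal dose, and events before dosing go to medical history (Section 6.1.8.1), so such a patient hardly enters these tables. This stands. The effect in the tables comes mainly from in-study reductions, which rest on investigator discretion within the stated range. A reader might infer that the protocol strictly requires stopping at 20 throughout the 48 weeks. The text says should, not must; Section 3.4 writes only an upper limit; and the taper text in the synopsis and Section 3.1.2 mentions doses at or below 20 mg/kg/day. Those passages need to be reconciled.
- *No dose comparison is planned.* The study is open-label and non-randomised, dose follows the previous study (Section 4.3), and there is no inference (Section 8.4.3). This stands, so no error rate is affected. But the tables are laid out by dose and carry no caution.
- *The information is not lost.* AE listings, TEAE tables by severity and relationship, and an exposure summary are planned. A reader might infer that dose reductions will go wholly unreported; the documents do not support that. What is missing is a summary.
- *The rates are assumed.* Section 1.3 gives 3 of 52 patients (about 6%) stopping for AEs or an SAE in the earlier extension. That counts discontinuations only, so it does not give the intolerance rate. With 10 patients per dose, 20% is two patients, so cells will be small.

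**Conclusion.** The point holds as a matter of interpretation. Section 8 tabulates by dose an outcome whose threshold differs by dose, and does not summarize the outcome that would balance it. Under equal 20% intolerance, counted by modal dose, the excess at 20 mg/kg/day is roughly 7 to 9 percentage points with 50% step-down and 11 to 14 with 80%. It vanishes without step-down.

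A reader might infer a fixed multiple, or that the lowest dose will always look worst. Neither follows. The size depends on intolerance, step-down and recurrence rates that the documents do not give, and on how modal dose regroups patients. With little step-down or a steep dose-response the order need not reverse. The dosing rule itself is not in question.

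**What to change.** In Section 8.4.3.1, or in the SAP that Section 8.4 says will be finalised before database lock, add descriptive tables of:

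1. AEs leading to dose reduction; and
2. AEs leading to dose reduction or discontinuation.

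Present each by dose at AE onset, with patients exposed at that dose (or their exposure time) as the denominator, and again by starting dose. Use the eCRF dose record to separate decreases from increases: the dose-modified category covers both, and the SAE action list in Section 6.1.8.5 has no dose-change category.

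Place these beside the modal-dose discontinuation table, with a note that discontinuation alone should not be compared across dose groups. Add no inferential dose comparison and change no dosing rule.

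The cost is one or two extra tables from data already collected. The cells will be small, and because doses are not randomised and tolerant patients may be titrated up, the by-dose results stay descriptive.

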### Study Assessments

At Visit 1 (Day 1) and each monthly and quarterly visit, the following assessments will be completed:

- Review of Antiepileptic Drugs (AEDs).
- Review of concomitant medications.
- Review of vital signs.
- Review clinical labs.
- Urinanalysis.
- Physical Examination (including height and weight).
- Brief Neurological Exam.
- Dispensing CBD.
- Drug Accountability.
- Review Adverse Events (AEs).
- 12-lead ECG.

At End of Study (Visit 7) or Early Withdrawal, the following assessments will be completed:

- Review of antiepileptic drugs (AEDs).
- Urinalysis.
- Urine pregnancy screen for post-menarchal females

 
• Review of concomitant medications.
 
• Review clinical labs
 
• 12-lead ECG.
 
• Review AEs.
 
• Review of vital signs
 
• Drug Accountability.
 
	
 
• Physical examination (including height and weight).
 
• Neurological examination
 
• Dispensing CBD.
 
• Columbia-Suicide Severity Rating Scale (C-SSRS).
 

--	--

At Taper Period (Visit 8), the following assessment will be completed:

- Collect CBD.
- Review AEs.

At Follow-Up (phone call only), the following assessments will be completed:

- Review of Antiepileptic Drugs (AEDs).
- Review of concomitant medications.
- Review AEs.

#### Taper Period

At the end of the Long-Term Safety study, patients will be tapered off of CBD over a 0-10 days period. The following tapering scheme will be utilized: 40 mg/kg/day will be reduced to 30 mg/kg/day for five days, then 20 mg/kg/day for five days, then stop; 30 mg/kg/day will be reduced to 20 mg/kg/day for five days, then stop; and doses  $\leq$  20 mg/kg/day can be discontinued without taper. This can be modified by the investigator based upon the patient's response.

Tapering will occur under the following circumstances:

- Patient completes Visit 7 (End of Study) of INS011-17-113
  - Patient will begin tapering the day after Visit 7
- Patient withdraws early
  - Patient will begin tapering the day after they decide to withdraw from the trial

#### Follow-Up Period

A Follow-up telephone call will occur 30 days after discontinuation of the study drug to assess AEs, AEDs, and record concomitant medications.

#### **Number of patients (planned):**

Up to 30 patients who completed INS011-17-103 will be enrolled in the study.

#### **Diagnosis and main criteria for inclusion:**

**Inclusion criteria**

1. Completed activities up to and including Visit 6 (End of Study) of INS011-17-103.
2. Patient and/or parent(s)/caregiver(s) fully comprehend the informed consent form (ICF) and assent form, understand all study procedures, and can communicate satisfactorily with the investigator and study coordinator, in accordance with applicable laws, regulations, and local requirements.
3. A female patient is eligible to participate in the study if she is:
  - a. Premenarchal, or
  - b. Of childbearing potential with a negative urine pregnancy test at the Screening Visit. If sexually active, she must agree to fulfill one of the following requirements:
    - i. Complete abstinence from intercourse for  $\geq$  4 weeks prior to administration of the first dose of the investigational product, throughout the Safety Period, and 4 weeks after completion or premature discontinuation from the investigational product, and agreement to use a double barrier method if she becomes sexually active.
    - ii. Use of acceptable methods of contraception throughout the study and 4 weeks after completion or premature discontinuation from investigational product. The acceptable method of contraception is double barrier method (i.e., condom plus spermicide or a condom plus intrauterine device [IUD], diaphragm, or stable hormonal contraceptive use for at least 3 months before screening and through 14 days after study completion).
4. A sexually active male patient or partner of enrolled patient must be willing to use acceptable methods of contraception throughout the study and for 4 weeks after completion of study participation or discontinuation from investigational product. The acceptable methods of birth control are abstinence or double barrier birth control (i.e., condom plus spermicide or a condom plus one of the methods listed in criterion #3).
5. In the opinion of the investigator, the parent(s)/caregiver(s) is (are) willing and able to comply with the study procedures and visit schedules, including venipuncture, and the visit schedules.

**Exclusion criteria**

1. Patient or parent(s)/caregiver(s) have commitments during the study duration that would interfere with attending all study visits.
2. Experienced an anoxic episode related to study drug requiring resuscitation during the previous study.
3. Developed an adverse event thought to be related to CBD in the previous study and for whom the Investigator determines that continuing treatment with CBD would not be in the best interest of the patient.

4. Evidence of other clinically significant disease such as unstable hepatic, hematological, renal, cardiovascular, gastrointestinal, immunological, or pulmonary diseases or ongoing malignancies.
5. Compromised respiratory function or severe respiratory insufficiency.
6. Clinically significant abnormal laboratory values within the past 14 days, including:
  - a. Liver function tests (LFTs) such as albumin, direct bilirubin, total bilirubin, aspartate aminotransferase (AST), and alanine aminotransferase (ALT)  $\geq 3$  times the upper limit of normal (ULN).
7. In the opinion of the investigator, the patient is unsuitable in any other way to participate in this study.

**Investigational product, dosage and mode of administration:**

Cannabidiol Oral Solution: an oral solution containing pharmaceutical grade synthetic cannabidiol manufactured and supplied by Insys Development Company, Inc.

Patients who completed INS011-17-103 will initiate this study on the dose with which they were receiving previously (20, 30, or 40 mg/kg/day orally). The total daily dose (mg/kg/day) will be administered in two equal doses (mg/kg) twice daily within 30 minutes after a meal. Doses of CBD may be adjusted at the investigator's discretion up to a maximum of 40 mg/kg/day once the higher dose level has been approved by the DMC in INS011-17-103.

Patients who withdraw early or complete this study will be tapered off in the following manner: 40 mg/kg/day will be reduced to 30 mg/kg/day for five days, then 20 mg/kg/day for five days, and then stop; 30 mg/kg/day will be reduced to 20 mg/kg/day for five days, then stop; and doses  $\leq 20$  mg/kg/day can be discontinued without taper. This can be modified by the investigator based upon the patient's response.

**Duration of treatment:**

The maximum duration of the study from Visit 1 (Day 1) to follow-up call will be approximately 54 weeks ( $\pm 3$  weeks).

**Reference therapy, dosage and mode of administration:**

Not applicable.

**Criteria for evaluation:**Safety Endpoints

- Incidence, type, and severity of AEs and serious adverse events (SAEs) associated with Cannabidiol Oral Solution (i.e., treatment-emergent adverse events [TEAEs]).
- Changes from baseline in vital signs, ECG findings, and laboratory values (hematology, chemistry, and urinalysis).
- Changes from baseline in neurological exam.

Baseline is defined as Visit 6 of INS011-17-103.

**Statistical Methods:**Safety Analysis

All safety assessments, including AEs, clinical laboratory evaluations, vital signs, 12-lead ECGs, physical examination (including height and weight), and neurological examinations will be listed for each visit. When appropriate, they will be summarized with descriptive statistics by age and dose cohort. The Medical Dictionary for Regulatory Activities (MedDRA; Version 20.0 or higher) will be used to classify all adverse events with respect to system organ class and preferred term. Adverse event summaries will include only TEAEs, which will be summarized for each treatment group.

- Clinical laboratory findings and vital signs will be summarized for all patients for observed values and change from baseline. Shifts from baseline to outside normal range criteria will also be presented for all patients.
- The neurological examination results will be listed and summarized descriptively. Shifts from baseline according to normal and abnormal criteria will also be presented for all patients.
- Results of physical examinations conducted throughout the study will be presented in listings and summarized descriptively. Shifts from baseline according to normal and abnormal criteria will also be presented for all patients.
- Concomitant medications and AEDs will be reported in the data listings.
- Statistical analyses will be performed using SAS® (Version 9.3 or higher, SAS Institute Inc.) or R (Version 3.3 or higher, Roswell Park Cancer Institute).

